#### TRIAL SIZE:

1500 RCS each consisting of multiple patients randomized 1:1 to control and intervention arms

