#### Hypotheses

Primary:

 The intervention results in a greater proportion of immediate ambulance responses in RCS being directed to the patient in the most critical condition as operationalized by subsequent NEWS value.

Secondary:

- The intervention improves differentiation with regards to a composite risk score consisting of ambulance interventions, abnormal initial ambulance findings, emergent transport, hospital admission, and mortality between patients receiving immediate vs. delayed ambulance response during RCS.
- 2. The intervention improves differentiation regarding NEWS between patients receiving immediate vs. delayed ambulance response during RCS.

Other pre-specified analyses:

- 1. Evaluation of overall personnel compliance with risk assessment instrument in intervention arm.
- 2. Evaluation of compliance in intervention arm cases where the model had a high vs low level of confidence.
- 3. Evaluation of improved/degraded compliance with risk assessment instrument over time as manifested by a slope change in a time series analysis of intervention group
- 4. Evaluation of spillover effects as manifested by a significant positive slope in a time series analysis of control group outcomes
- 5. Evaluation of change in risk assessment tool predictive value over time (covariate drift)
- 6. Evaluation of model calibration with regards to age, gender, and complaint category

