## Setting

The study will take place in two EMDCs in central Sweden (Uppsala and Västmanland), serving a combined population of 499 000. The regions have a total of 32 ambulances during peak hours. Each dispatch center is staffed by 2-3 nurse call-takers and 1 ambulance director 24 hours per day. The

study has been piloted and initiated in the region of Uppsala, and Västmanland will join the study contingent on the collection of outcome data necessary to train and validate the risk assessment models.

In these regions during 2020, ca. 30% of callers received a high priority lights and sirens response, ca. 43% of patients received a low priority response, 5% were inter-facility transfers, and 22% of callers were referred to non-ambulance care. The median time from receipt of call to dispatch of ambulance (the "dispatch time") for low-priority ambulance responses was 18 minutes, and the median response time was 37 minutes. The dispatchers currently employ a self-developed, rule-based Clinical Decision Support System (CDSS) to structure patient interviews and determine a priority level, as described elsewhere (5,6).

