## Data management / Collection

Data collected by EMDCs regarding dispatcher decisions, machine learning model predictions, treatment group allocation, etc., will be stored in the currently employed dispatch system database used by both Uppsala and Västmanland to limit exposure of patient data. Database queries will be performed against this database, and combined with ambulance and hospital data collected in an

existing database used for quality assurance/improvement at Region Uppsala. Similar queries will be developed to extract ambulance and hospital data from Region Västmanland, and the need to develop these data extraction processes entails that Västmanland will begin including patients to the study after Region Uppsala. Manual data entry will be performed only to correct errors, and random spot-checks of data quality will be performed. These processes will be similar to those employed to generate the data used in the retrospective study validating the methods used here. (1)

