## Statistical analysis

To generate risk predictions, gradient boosting models are applied to patient demographics, structured CDSS data, and free-text noted embedded using the bag-of-words method. The methods are implemented in the openTriage platform as the 'uppsala\_alitis' framework (13) and have been validated in previous research.

The primary hypotheses will be evaluated using a standard two-sided test of proportions between the intervention and control groups. Investigating the secondary hypotheses will involve comparing outcomes for the patient receiving an ambulance immediately with patients for whom dispatch is delayed. Patients who do not receive an ambulance immediately may also potentially be included in later trials. This induces a potential that information from intervention arm comparisons could be used by dispatchers in control arm comparisons, thus biasing the results in the direction of a smaller intervention effect. Steps were taken in the development of the user interface to limit these "spillover" effects.

Figure 1 – Analysis flow

Additional pre-specified analyses 1-2 will be investigated by assessing the compliance of dispatchers with the risk assessment tool of risk scores in the high and low confidence groups of the intervention arm (calibrated based on pilot study data to consist of ca. 50% of assessments each), as well as dispatcher compliance, with the hypothesis that compliance will be higher in the high-confidence group.

Pre-specified analyses 3-5 will be examined using time-series analysis within a regression framework employing a variable representing the study month as the independent variable of interest. Analysis 6 will be conducted by constructing calibration curves for the risk model based on the patient groups of interest.

Missing vital sign data will be imputed using Multivariate imputation by chained equations. (14) As we found previously that between-imputation variance after calculating NEWS scores was minimal, the median of 5 imputed NEWS values will be used to assess the primary hypothesis. An analysis of loss to follow-up (i.e., patients requesting to withdraw from the study) will be performed.

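### Analyses 3-5 regress on study month with no centre term although Västmanland starts after Uppsala, so a stable difference between centres can appear as, or mask, a change over time

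*Combined protocol and SAP*

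**What the plan says.** All references are to the combined protocol and SAP.

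- **Entry of centres.** Under Setting, the study is already piloted and running in Uppsala, while "Västmanland will join the study contingent on the collection of outcome data necessary to train and validate the risk assessment models". Data management / Collection repeats that "Västmanland will begin including patients to the study after Region Uppsala". No entry date is given.
- **Questions asked.** Under Hypotheses, analysis 3 looks for altered compliance, "manifested by a slope change in a time series analysis of intervention group". Analysis 4 is "Evaluation of spillover effects as manifested by a significant positive slope in a time series analysis of control group outcomes". Analysis 5 asks whether the tool's predictive value changes over time.
- **Method.** Statistical analysis handles all three with a "time-series analysis within a regression framework employing a variable representing the study month as the independent variable of interest". The readable text mentions no centre term, centre-specific series, Uppsala-only analysis or time since centre entry. It does not say where the count of study months begins.
- **Size.** The Abstract gives "1500 RCS each consisting of multiple patients randomized 1:1 to control and intervention arms". Sample Size caps data collection at 2 years.

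**The concern.** If month counts from trial start, the early months contain only Uppsala and the later months contain both centres. A constant gap between the centres then tilts the month slope although nothing changes at either one. Randomisation gives no protection, because analyses 3 and 4 follow a single arm over time and analysis 5 follows the model.

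The plan reads these slopes as mechanisms. A less compliant late centre could pass for declining compliance. A late centre with better control-arm accuracy could pass for spillover, and one with worse accuracy could hide real spillover. A weaker model at the late centre could pass for drift. Analysis 4 matters most for interpretation: Statistical analysis says spillover would shrink the measured intervention effect, and analysis 4 is the plan's check for it.

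**Working it through.** **Plan's own figure.** The plan gives no power or error rate for analyses 3-5. Its primary power figure does confirm the size per arm. With 63.5% vs 70.3%, 750 per arm and two-sided α = 0.05 (assumed to carry over from the Wilcoxon calculation):

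- null SE = √(2 × 0.669 × 0.331 / 750) = 0.02430
- alternative SE = √((0.635 × 0.365 + 0.703 × 0.297) / 750) = 0.02424
- power = Φ((0.068 − 1.96 × 0.02430) / 0.02424) = Φ(0.84) = 0.80, as stated.

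**Inputs.** From the documents: 750 RCS per arm, 24 months, control accuracy 63.5%. Assumed, because the documents give no values: entry at month 7 or 13; late-centre share s of 40% or 20% once it joins; constant total monthly intake; compliance 80% at Uppsala; gap D of 5 or 10 points; no trend within either centre.

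**Bias in the slope.** Omitting centre gives an expected slope of D × cov(month, centre) / var(month).

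- var(month) = (24² − 1)/12 = 47.92.
- cov = s × π(1 − π) × 12. Here π is the fraction of RCS from the entry month on, and 12 is the distance between the mean month before and after entry (3.5 vs 15.5, or 6.5 vs 18.5).
- At s = 0.40, entry at month 7 gives 0.40 × 0.75 × 0.25 × 12 = 0.90. Entry at month 13 gives 0.40 × 0.50 × 0.50 × 12 = 1.20.
- For D = −10 points the slope is −0.10 × 0.90/47.92 = −0.00188 per month, or −0.10 × 1.20/47.92 = −0.00250. Over 23 monthly steps this is −4.3 or −5.8 points.

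**Chance of a significant slope.** SE ≈ √(p(1 − p)/(750 × 47.92)), where p is the pooled proportion, and z = slope/SE.

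| Scenario | Entry month | z | Closed form | Simulated |
|---|---|---|---|---|
| Compliance 80% vs 70%, s = 40% | 7 / 13 | −0.85 / −1.15 | 13.5% / 20.9% | about 14-22% |
| Compliance 80% vs 70%, s = 20% | 7 / 13 | −0.43 / −0.58 | 7.2% / 9.0% | 7-10% |
| Compliance 80% vs 75%, s = 40% | 7 / 13 | −0.43 / −0.58 | 7.2% / 9.0% | 6-10% |
| Control 63.5% vs 73.5%, s = 40%, positive slope only | 7 / 13 | 0.75 / 1.00 | 11.4% / 16.8% | about 12-16% |

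The nominal rate is 5% in the first three rows and 2.5% in the last. Halving either the share or the gap halves the bias, so rows two and three agree. With control accuracy of 63.5% vs 53.5%, the false trend is about 4 to 6 points downward, which would mask spillover.

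**Sensitivity to intake.** Suppose Uppsala's monthly intake stays constant and Västmanland adds to it. Then π becomes 30/36 or 20/32, cov becomes 0.667 or 1.125, and var becomes 42.92 or 45.67. The first row falls to 10% or 19%.

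**With a centre term.** Simulated two-sided rejection returns to about 5%, and the mean apparent trend to about zero.

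**If month counts from centre start.** Centre and month are still correlated, with the opposite sign. At s = 40%, Västmanland's RCS average month 9.5 (entry at 7) or 6.5 (entry at 13). Uppsala's average (6 × 3.5 + 10.8 × 15.5)/16.8 = 11.2, or (12 × 6.5 + 7.2 × 18.5)/19.2 = 11.0. Redefining the clock therefore does not remove the problem without a centre term.

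**Limits.** These figures test for a non-zero linear slope, whereas analysis 3 speaks of a slope change. Analysis 5 was not simulated; the same mechanism applies, but its size is not quantified here.

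**The case against.** Several points on the other side stand.

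- **Calendar time is not stipulated.** A reader might infer that the plan fixes calendar month. The text says only study month and leaves its origin undefined.
- **Silence is not exclusion.** Naming month as the variable of interest leaves room for covariates. The Blinding section promises published code, written where possible before final extraction, and the analysis-flow figure could not be read for this check. What can be said is that no centre adjustment is specified.
- **The effect is conditional.** A reader might infer that analyses 3-5 will give wrong answers. They will not if Västmanland never joins or does not differ. The documents give no between-centre difference, and entry depends on having the data to train and validate the models, which makes a weak model at entry less likely. Flow says the tool is integrated at all centres before the study starts. Even at a 10-point gap and 40% share, most simulated trials show no false slope, and at 5 points the rates are close to nominal.
- **The main results are not biased this way.** A reader might carry the concern over to the primary or secondary comparisons. RCS are randomised 1:1 at the time of inclusion, so both arms recruit concurrently at whichever centres are active.
- **A change of clock is not the remedy.** Months since centre start equals study month minus a constant for each centre. Once centre is in the model, a common linear slope is the same on either clock. Drift in analysis 5 is plausibly a calendar process, since models are updated and reviewed quarterly.

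None of this removes the core point: staggered entry is planned, the slopes are to be read as mechanisms, and nothing specified separates centre from time.

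**Conclusion.** The concern holds in a conditional form. As written, analyses 3-5 do not separate a constant difference between centres from a change over time, and the time variable is undefined. If Västmanland joins late and differs by 10 points while supplying 40% of RCS, a false compliance slope arises in about 14-22% of trials (10-19% if intake grows on joining). A false sign of spillover arises in about 12-16%, against a nominal 2.5%. With a 5-point gap or a 20% share, the compliance figure is only about 6-10%. Entry month, share, intake pattern, compliance level and gap are all assumptions. The matter is confined to secondary-tier questions and does not bias the randomised comparisons. It should still be changed, because analysis 4 will inform how the primary result is read.

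**What to change.** In Statistical analysis, for analyses 3-5:

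1. Include a centre term in each regression, so that the month slope is estimated within centre.
2. Define study month, stating whether it counts from trial start or from the centre's start.
3. Show centre-specific slopes, including Uppsala alone.
4. Optionally, show months since centre start as an addition for learning in analysis 3, where the trend is not linear or slopes differ by centre. Keep calendar month within centre for drift in analysis 5.

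This takes a sentence or two and no new data. The cost is some precision in the pooled slope if the centres do not differ. At a 40% share, the squared correlation of month and centre is 0.90²/(47.92 × 0.30 × 0.70) = 0.08 for entry at month 7, or 1.20²/(47.92 × 0.20 × 0.80) = 0.19 for month 13. The SE therefore rises by a factor of 1/√0.92 = 1.04 or 1/√0.81 = 1.11.

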#### OUTCOMES:

Primary:

1. Proportion of RCS where the first available ambulance was dispatched to the patient with the highest National Early Warning Score (NEWS) score

Secondary:

- Difference in composite risk score consisting of ambulance interventions, emergent transport, hospital admission, intensive care, and mortality between patients receiving immediate vs. delayed ambulance response during RCS.
- Difference in NEWS between patients receiving immediate vs. delayed ambulance response during RCS.

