#### Outcomes

The primary outcome of the study is based on the National Early Warning Score (NEWS) of each included patient based on the first set of vital signs captured by the ambulance crew upon arrival to the patient. If Ambulance vitals signs are missing (e.g., if a patient opted to take an alternate mode of transport to the hospital), the first set of vital signs obtained at ED triage will be used. NEWS was selected as the primary outcome of the study for two reasons: Firstly, NEWS is widely used in acute care, and has been thoroughly validated as being predictive of outcomes in a variety of adult patient cohorts.(7–10) Secondly, NEWS is based on patient vital signs, and is thus conceptually distinct from-, and prior in terms of causality to the outcome measures we employ to train the predictive models.

The latter reason is a subtle but important conceptual point which addresses two issues: Firstly, by selecting an evaluation measure which is not causally dependent on (or indeed identical to) the outcomes used to train the models, we minimize the possibility that assignment to the intervention or control arm in and of itself affects the evaluation measure (e.g., if it were communicated to the ambulance crew that a patient had a high risk of transport to the hospital using lights and sirens, this could influence the decisions of the crew, perhaps making them more likely to do so). Secondly, it addresses issues relating to AI system alignment. As suggested by the orthogonality thesis, the predictive performance of an AI system is independent of the goals of the system as a whole. (11) Operationalizing the need for a rapid ambulance response in terms of measurable outcomes is difficult, and we cannot assume that we have done so perfectly. Thus, it is appropriate that both the model and human decisions are evaluated in terms of a measure which in causally independent of either. In this way, we avoid giving the ML framework an unfair advantage over human dispatchers who may have internalized a different definition of patent risk and ambulance care need.

The first secondary outcome in the study is based on a composite score consisting of each of the four outcomes included in the risk assessment instrument. The outcomes will be weighted in a manner identical to the prediction framework. While this measure of intervention effectiveness suffers from

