## Sample Size

Given the prevalence and diversity of non-clinical determinants in resolving RCS, the actual retrospective accuracy of dispatchers in identifying the most critically ill patients could not be determined. Instead, sample size was determined using a simulation-based approach. Low-priority calls are divided into 2 categories – 2A and 2B. A simulation was performed under the assumption that a priority 2A call would always be selected for immediate ambulance dispatch over a priority 2B call, and that dispatchers would have 100% compliance with the machine learning tool.

Based on 1000 bootstrap resampled pairs of patients ranked using either dispatch category or the ML framework, a U-statistic of 0.545 in favor of the ML framework was identified. This resulted in required sample size of 1500 at  $\alpha$ = 0.05,  $\beta$  = 0.85, and a randomization ratio of 1:1 for a Wilcoxon–Mann–Whitney test of difference in central tendency. (12) Based on an estimate of 2 RCS per day meeting all inclusion criteria, an upper bound on the data collection duration was set to 2 years.

Upon further refinement of the prediction models over the course of the pilot study, it was found that this difference-based test had an excess of power, and a more conceptually simple but less sensitive formulation of the primary hypotheses was adopted. Pilot study data indicate that RNs direct the available ambulance to the patient with the highest NEWS score 63.5% of the time (considering ties as "correct" assessments), while simulations suggest that the model will mark the patient with the highest NEWS correctly in 70.3% of cases, resulting in an estimated power of 0.8 at n=1500 using a two-sided test of proportions.

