## Monitoring

All dispatch system data will be collected within a single IT infrastructure under the direct supervision of the PI. Outcome data will be collected either directly by the research group, or in close cooperation with the research group in the case of Västmanland. Randomly sampled outcome data will be manually checked to ensure quality. The research group will conduct regular follow-ups with dispatchers responsible for executing the study protocol to ensure compliance.

A data monitoring committee (DMC) consisting of the medical directorship of the ambulance services and dispatch centers in the two studied counties will handle adverse events (AEs) and make decisions regarding early trial stoppage. Early stopping will be evaluated quarterly based on the Haybittle–Peto rule, with a p-value of <0.01 bounding an effect regarding the primary hypothesis. (15) If this threshold is reached, the treatment group will be unblinded to determine if the effect is detrimental, in which case the study will be halted to ensure patient safety. No early stopping rule for a beneficial effect will be employed.

Theoretical model performance will be evaluated as part of the quarterly DMC reviews. If theoretical model performance is found to suffer from a significant reduction in performance during a given month, hyperparameter optimization will be attempted. If theoretical model performance degrades beyond the point at which a clinical benefit from the intervention can reasonably be expected, a decision by the DMC to pause the trial until the issues can be corrected may be taken. Any changes to model hyperparameters or the estimation framework will be noted in the manuscript, and be made available for peer- and public review.

The existing adverse event reporting system in both counties will be monitored by the DMC for AEs relating to the patients included in the trial. Any AEs reported by patients or providers will be evaluated by the DMC.

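### A patient found dead or in cardiac arrest with no recorded vital signs would be given an imputed NEWS, so that RCS can be misclassified in the primary outcome in either direction

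*Combined protocol and SAP*

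**What the plan says.** The primary outcome (Abstract, Outcomes) is "Proportion of RCS where the first available ambulance was dispatched to the patient with the highest National Early Warning Score (NEWS) score". The Outcomes section of Methods sets the source of the score: it is "based on the first set of vital signs captured by the ambulance crew upon arrival to the patient", and if those are missing, "the first set of vital signs obtained at ED triage will be used". The one example of missingness given there is a patient who travelled to hospital by other means.

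Statistical analysis deals with what is left: "Missing vital sign data will be imputed using Multivariate imputation by chained equations", and "the median of 5 imputed NEWS values will be used to assess the primary hypothesis". The reason given for using a median is that variance between imputations was found to be minimal in earlier work. The imputation predictors are not listed. The only loss to follow-up named is withdrawal at the patient's request.

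Under Sample Size, the pilot rate of 63.5% was computed "considering ties as 'correct' assessments". Under Monitoring, the quarterly early-stopping check uses the same endpoint, "with a p-value of <0.01 bounding an effect regarding the primary hypothesis".

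**The concern.** The chain of ambulance values, ED values, then imputation has no branch for a patient whose vital signs are absent because there were none to measure. Standard MICE treats missing values as predictable from what was observed. Here the absence itself carries the information, and nothing in the plan shows that death or arrest would inform the imputed score. Low between-imputation variance does not answer this, because it says nothing about bias when missingness depends on the patient's state. Taking a median of five also pulls the score away from the extremes.

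The Objectives section sets the aim as dispatch to the most critically ill patient. A rule that can score a delayed patient found dead as a correct dispatch, or an immediate dispatch to a patient in arrest as a wrong one, works against that aim for the patients where the answer is clearest. The quarterly check uses the same endpoint and inherits the same scoring.

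**Working it through.** **1. The plan's own figure.** Inputs from Sample Size: 63.5% (pilot), 70.3% (simulated), 1,500 RCS at 1:1, so 750 per arm. Two-sided α = 0.05 is stated for the earlier rank test and assumed to carry over.

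- Pooled rate = 0.669; SE under the null = √(2 × 0.669 × 0.331 / 750) = 0.0243.
- SE under the alternative = √((0.635 × 0.365 + 0.703 × 0.297) / 750) = 0.0242.
- Power = Φ((0.068 − 1.96 × 0.0243) / 0.0242) = Φ(0.84) = 0.80.

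The stated 0.8 reproduces. The planned difference is 6.8 points.

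**2. How often one such RCS is mis-scored.** The documents give no NEWS distribution. Assume two patients per RCS, a skewed NEWS (negative binomial, size 1.2, capped at 20) with mean 1.5, 2.5 or 3.5, imputed values drawn from the same distribution, and ties counted as correct. Let M be the median of five draws and X the other patient's NEWS.

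| Mean NEWS | Delayed patient unmeasured: scored correct, P(X ≥ M) | Immediate patient unmeasured: scored incorrect, P(X > M) | P(M ≥ 7) |
|---|---|---|---|
| 1.5 | 65% | 39% | 0.01% |
| 2.5 | 59% | 42% | 0.6% |
| 3.5 | 57% | 44% | 3.6% |

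A single draw would reach 7 or more in 2–17% of cases, so the median makes a high imputed score rarer.

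**3. Number of RCS.** Assume 1,500 × 2 = 3,000 patient entries, of which 0.1–0.5% are dead or in arrest with no vital signs: 3–15 patients, each in a different RCS.

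- All delayed: 3 × 0.57–0.65 = about 2; 15 × 0.57–0.65 = about 9–10 RCS wrongly scored correct.
- Fifteen split evenly by status: 7.5 × 0.57–0.65 = 4.3–4.9 wrongly correct, and 7.5 × 0.39–0.44 = 2.9–3.3 wrongly incorrect. About 8 are mis-scored in all. Net, from 7.5 × (0.567 − 0.442) to 7.5 × (0.648 − 0.392), is about 1–2 RCS across both arms.

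**4. Extreme case for the arm contrast.** Start from the planned rates (476/750 against 527/750, p = 0.005) and move k RCS from correct to incorrect, all in the intervention arm: k = 1 gives p = 0.006, k = 4 gives 0.010, k = 8 gives 0.019. Eight RCS is 8/750 = 1.1 points against 6.8. This needs nearly every affected patient to be a delayed patient in one arm.

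**5. The quarterly rule.** At the expected 2 RCS per day, one quarter yields about 180 RCS, or 90 per arm. With control at 63.5% (57/90), p<0.01 needs an intervention deficit of 18: 39/90 gives z = 2.69, p = 0.007, while 40/90 gives p = 0.011. The deficit needed is 25 at 180 per arm, 35 at 375 and 49 at 750.

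**The case against.** The best case against has four parts.

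- **Scope.** MICE is applied to missing vital signs, not to whole scores, so any recorded component is kept and informs the rest. The documents do not say what crews record in an arrest, and a predictor set that included outcome data could raise the imputed score. This stands, and it limits the point to patients with no vital signs from either source.
- **Size.** The frequency is assumed, the errors run both ways, and the same rule applies in both arms. This also stands. A reader might infer that the primary result is materially biased, or biased in favour of the intervention. The documents do not support that: they give no count and no reason to expect a difference by arm.
- **Safety.** A reader might infer that the stopping rule is disabled or reversed by such deaths. The deficits in step 5 show that a few RCS would rarely decide it, however they are scored. Death within 30 days also counts in the composite secondary outcome, and the DMC monitors and evaluates adverse events and decides on early stopping. The event is lost to the primary outcome and its trigger, not to the trial.
- **Remedy.** NEWS was chosen because it is distinct from, and causally before, the outcomes used to train the models; a maximum score for death could be said to bring a training outcome into the endpoint. This is weak. Arrest or death at first contact is the patient's state at the moment NEWS is measured, not a later result of crew decisions. It does rule out 30-day death as the identifier, because that does not show the state at first contact.

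**Conclusion.** The point holds in limited form. Read literally, the plan gives a modelled NEWS to a patient found dead or in arrest with no recorded vital signs, and the RCS can then be misclassified in either direction. This is a stated rule that gives the wrong score for that patient, and not merely missing detail. Under the assumed 0.1–0.5% frequency and NEWS distribution, about 2–10 of 1,500 RCS would be affected. The net shift is perhaps 1–2 RCS if immediate and delayed patients are equally represented, and more if delayed patients predominate or such cases differ by arm. The planned sample size does not change. The correction is worth making because it brings the primary outcome closer to the trial's stated aim, and because settling it beforehand avoids a decision about deaths after the data are seen.

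**What to change.** Add one rule to Outcomes and Statistical analysis: a patient documented as dead or in cardiac arrest at first ambulance (or ED) contact, without a measured set of vital signs, is scored as the worst state (maximum NEWS) in the primary analysis and in the quarterly check. Keep MICE, with the median of five, for all other missing vital signs. Report the number of such patients by arm and by immediate or delayed status, and give the MICE-only result as a sensitivity analysis.

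The cost is small but not nil. A fixed value replaces a modelled one for a handful of patients. The cases must be identified from the ambulance records, and the documents do not show that a coded field for this exists, so some record review may be needed. Identification should be done by someone blind to arm and written into the analysis code before final extraction, in line with the intention under Blinding.

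### Reducing five imputations to one median NEWS per patient leaves imputation uncertainty out of the primary standard error; the harm depends on how many whole vital-sign sets are missing, a rate the plan does not give

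*Combined protocol and SAP*

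**What the plan says.** The Statistical analysis section of the combined protocol and SAP sets out three steps:

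- "Missing vital sign data will be imputed using Multivariate imputation by chained equations".
- NEWS is then calculated and "the median of 5 imputed NEWS values will be used to assess the primary hypothesis". The same sentence gives the reason: earlier work found minimal between-imputation variance in NEWS. No figure is given.
- "The primary hypotheses will be evaluated using a standard two-sided test of proportions between the intervention and control groups". No variance adjustment for imputation is mentioned.

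The Outcomes section describes a step before imputation. It opens "If Ambulance vitals signs are missing (e.g., if a patient opted to take an alternate mode of transport to the hospital", and goes on to substitute the first vital signs taken at ED triage. Imputation is therefore needed only where the ED-triage values do not fill the gap.

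The primary endpoint is binary per RCS: did the first available ambulance go to the patient with the highest NEWS? In the planning figures, ties count as correct.

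The documents do not give the missing-data rate, the between-imputation variance, the variables in the imputation model, or any pooled or sensitivity analysis.

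**The concern.** Taking one median per patient turns multiple imputation into single imputation with a smoothed value. The test then treats that value as measured, so the main benefit of generating several imputations is given up.

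The plan's reason does not reach the endpoint. Low variance in individual NEWS values does not establish low variance in a within-RCS ranking, where a one-point change can make or break a tie. Take a two-patient RCS with one incomplete patient. If three of the five imputations make the dispatch correct and two do not, the median scores a full success, whereas averaging over the imputed datasets gives 3/5 = 0.6. The split, which is the uncertainty, disappears.

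Missingness may also differ between the patients being compared. It is plausible, though not stated, that patients who wait are more likely to travel by other means and so lack ambulance vital signs. At stake is an interval around the primary difference that could be too narrow, in a design with no spare power.

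**Working it through.** **1. The plan's own power figure.** Inputs from Sample Size and Trial Size: control 0.635 ("RNs direct the available ambulance to the patient with the highest NEWS score 63.5% of the time"), intervention 0.703 ("the model will mark the patient with the highest NEWS correctly in 70.3% of cases"), and 1500 RCS allocated 1:1, so 750 per arm. Two-sided alpha of 0.05 is stated for the earlier rank test and assumed to carry over.

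- Mean proportion = (0.635 + 0.703)/2 = 0.669.
- Null SE = √(2 × 0.669 × 0.331/750) = 0.0243.
- Alternative SE = √[(0.635 × 0.365 + 0.703 × 0.297)/750] = 0.0242.
- Power = Φ[(0.068 − 1.96 × 0.0243)/0.0242] = 0.7997.

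This reproduces "resulting in an estimated power of 0.8 at n=1500 using a two-sided test of proportions". The calculation makes no allowance for missing data.

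**2. What ignoring the uncertainty could cost, by formula.** Let f be the fraction of missing information (assumed, since the documents give none). The correct SE is the naive SE × 1/√(1 − f). If the naive SE is too small by that factor, type I error is 2Φ(−1.96√(1 − f)). Power with the correct SE uses 750(1 − f) per arm.

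| f | SE above naive | Type I error if ignored | Power with correct SE |
|---|---|---|---|
| 1% | 0.5% | 0.051 | 0.796 |
| 2% | 1.0% | 0.052 | 0.792 |
| 5% | 2.6% | 0.056 | 0.779 |
| 10% | 5.4% | 0.063 | 0.757 |
| 20% | 11.8% | 0.080 | 0.707 |

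**3. Simulation with a real effect and whole NEWS values missing.** Missing rates, score distributions and imputation strength are assumptions. Arm and dispatch decision are in the imputation model.

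- A: 1500 two-patient RCS, predictor correlation 0.5, true difference about 6.3 points, 1500 replicates.
- B: the same layout and correlation, but integer scores, predictive mean matching, true difference about 9.4 points, 1200 replicates.
- C: a further run under its own assumed inputs.

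Entries are for the median of five: reported SE against actual SD, and coverage of the 95% interval where available.

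| Missing (immediate / delayed) | A | B | C |
|---|---|---|---|
| 2% | – | 0.0234 vs 0.0231, 95.5% | about 94% |
| 5% | 0.0236 vs 0.0243 | 0.0234 vs 0.0238, 94.8% | about 94% |
| 5% / 15% | 0.0235 vs 0.0250 | 0.0233 vs 0.0244, 93.4% | 93% |
| 10% / 30% | 0.0234 vs 0.0268, 91.7% | 0.0232 vs 0.0262, 91.3% | 0.0222 vs 0.0252, 91% |

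In the last row the SE shortfall is 1 − 0.0234/0.0268 = 13% in A, 1 − 0.0232/0.0262 = 11% in B and 1 − 0.0222/0.0252 = 12% in C. Rubin pooling gave coverage of 96–97% in A, 95.7–96.7% in B and 95–97.5% in C.

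**4. Simulation with single vital signs missing.** The plan imputes components, so this case matters. Assumptions: seven scored components, true difference about 5.8 points, arm and decision in the model, 1000 replicates.

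- 10% of each sign missing, so 1 − 0.9⁷ = 52% of patients have something imputed: SE 0.0234 vs SD 0.0232, coverage 95.3%. Pooling over-covered at 97.8%.
- 2% / 6% of whole sets plus 2% of each sign missing: coverage 94.0%.
- 5% / 15% of whole sets plus 5% of each sign missing: coverage 91.7%.

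The shortfall follows whole-set missingness.

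**5. Type I error of the median-of-five test.** 3500 null replicates, Monte Carlo error about 0.004, whole NEWS missing completely at random.

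| Missing | Imputation model | Type I error |
|---|---|---|
| 2% | strong, with arm | 0.048 |
| 10% | strong, with arm | 0.050 |
| 10% | weak, with arm | 0.047 |
| 20% | weak, with arm | 0.061 |
| 30% | weak, with arm | 0.070 |
| 20% | weak, without arm | 0.052 |

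In these runs Rubin's rules were conservative (type I error 0.014 to 0.047), so the gap between the naive and Rubin SEs overstates the true shortfall.

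**6. Leaving arm and decision out of the imputation model.** With the median, the effect in A shrank from 6.3 to 6.1, 5.9 and 5.5 points at 5%, 5% / 15% and 10% / 30% missing. In B it went from about 9.5 to 8.3 at 10% / 30%. Pooling with the same omission did not cure this.

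**The case against.** The best defence is that the plan gives a reason, and under that reason the point is close to nil. If the fraction of missing information is up to 2%, the SE is out by about 1%. The ED-triage substitution reduces whole-set losses before imputation starts, and where only single signs are missing the interval was sound and pooling too wide. The larger shortfalls need missing rates that nothing in the documents supports. All of this stands, and it limits the size of the point. It does not make the rationale adequate: minimal is never quantified, and it was judged on scores rather than on the RCS-level result.

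Two stronger readings are tempting.

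- **That the primary standard error is too small as a matter of fact, or the test invalid.** The documents give no missing rate, and simulated type I error stayed at 0.047–0.050 up to 10% missing. It rose clearly only at 20–30% of whole NEWS values missing with a weak imputation model that included arm.
- **That taking the median shrinks the treatment effect.** The shrinkage comes from omitting arm and dispatch decision from the imputation model. The plan does not say they are omitted, and pooling would not repair it.

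**Conclusion.** The point holds conditionally. The primary analysis as written carries no imputation uncertainty, and the reason offered does not cover the binary ranking endpoint. Under the assumed scenarios:

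- Negligible with about 5% or less of whole vital-sign sets missing after the ED-triage fallback (at most about one percentage point of coverage), or with only single components missing.
- Coverage about 93% at 5% immediate / 15% delayed, and 91.7% when a further 5% of each single sign was also missing.
- SE roughly 11–13% too small and coverage about 91–92% at 10% / 30%.

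These figures rest on assumed NEWS distributions, two-patient RCS, assumed missingness patterns, and arm and decision in the imputation model. Importance is minor to moderate.

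**What to change.** - **Primary analysis.** In each imputed dataset, calculate NEWS, derive the RCS success indicator and estimate the difference in proportions. Combine estimates and variances with Rubin's rules. Keep the median approach as a sensitivity analysis.
- **Imputation model, a separate point.** List its variables. Include study arm, immediate/delayed status and their interaction. Using the randomized arm code already planned under Blinding keeps the analyst blind.
- **Reporting.** Give the missing rate after the ED-triage fallback, by immediate/delayed status and separately for whole sets and single signs. Give the between-imputation variance of the RCS-level indicator.

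The cost is a few lines of code and a short SAP edit; the five imputations are already planned. The interval becomes slightly wider and mildly conservative. If between-imputation variance is as small as the plan says, the result barely changes. If much is missing, the widening is larger and power falls below the planned 0.8.
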